## Procedures

The research will be carried out in four stages: Preparation for the study, design and adjustment of instruments, data collection and data analysis. Ordered according to the logical steps to follow within the development of obtaining the required data.

### **Phase 1: Preparation for the study**

In this stage, the search for initial information will be carried out, for this a bibliographic review will be carried out for the present study that includes research published in different databases, related to the validation and comparison of medical devices, the use of the EIT and the studies related to the use of respiratory incentive in the clinical setting and its levels of evidence. Once this is done, the research approach, the study design, the form of selection and sample size, and the writing of the document will be carried out.

For the development of this study, the main researcher will carry out a 24-hour training in the handling of the equipment with the personnel of the commercial house. (Drager).

The informed consent will be designed and the written research work will be sent to the ethics committee to receive endorsement.

### **Phase 2: Design and Adjustment of Instruments**

The data collection instrument will be designed.

For the standardization of anthropometric measurements (weight and height), Standardized Operating Procedures 1 and 2 will be used according to the instructions defined in these

For the measurement of the EIT, the Standardized Operating Procedure 3 designed for projects previously carried out by GIESC will be used. "Effect of two lung reexpansion techniques on the ventilation of participants undergoing cardiovascular surgery. Controlled clinical trial phase II b"

The pilot test will be carried out with 5 healthy subjects who will not be part of the sample, they will be informed about the research, they will be asked to sign the informed consent and the measurements and data collection will be carried out with the designed data

collection format. by the researcher. Said pilot test will be carried out to test and make pertinent corrections in the management of the evaluation instruments and in order to identify the times required in the measurement of the variables.

### **Phase 3: Data Collection:**

#### **Call for participants**

For the recruitment of healthy volunteers between 18-65 years of age in the community of Santiago de Cali, taking into account the social distancing established by the current COVID 19 pandemic, direct contact will be made with people from the administrative areas of the Universidad del Valle , from the research groups of the Universidad del Valle, family and friends who will initially be provided with information about the objectives of the research and will be invited to participate.

Social networks will also be used to send information about the research and the contacts (email, cell phone) of the researchers will be left so that people interested in participating can register.

People who decide to register to be included in the study will be contacted and the date, time and place will be organized, taking into account the availability of time, as well as the capacity and the biosafety protocols established in the places where they will be carried out. the measures. The EIT will be performed in the movement laboratory located at the Universidad del Valle and the spirometries at the Hospital Universitario del Valle.

#### **Data collection protocol**

##### **Before performing spirometry**

If the subject is eligible, a series of recommendations will be made that must be taken into account prior to arrival to take measurements:

1. Not having done physical activity in the last 12 hours prior to the exam.
2. Not having smoked cigarettes in the last 12 hours prior to the exam.
3. Do not consume caffeinated beverages on the day of the exam
4. Comfortable clothes

##### **Performing spirometry**

This measurement will be carried out at the Hospital Universitario del Valle, in the physical medicine and rehabilitation unit in the pulmonary function laboratory with the medgraphics cardiorespiratory diagnostics® brand spirometer that belongs to the Universidad del Valle and is under the custody of the Hospital Academic. The spirometries will be carried out by the researcher, who is a physiotherapist specializing in cardiopulmonary physiotherapy. The day of the test will begin with the completion of the informed consent, this will be read and explained to the participant and will continue to the signature. On this day, the researcher will fill out the sociodemographic data of the participant, weight and height measurement, Charlson index and IPAQ abbreviated questionnaire, according to the instructions defined in the Standardized Operational Procedures 1, 2, 4 and 5 for these procedures in the data collection format. data.

Spirometry will be performed according to the institutional protocol of the Hospital Universitario del Valle. The duration of this procedure will take approximately 1 hour

### **Randomization**

The randomization to choose which will be the first incentive that each participant will use and to which the first ventilation measurement will be carried out by means of EIT, will be carried out by simple randomization, through the "RANDOM.ORG" program (<https://www.random.org/lists/>) and <http://www.jerrydallal.com/random/permute.htm>

These measurements will be made at the facilities of the Universidad del Valle, according to availability. The first measurement will be carried out with the incentive that has been randomly assigned to the participant, the second measurement will be carried out one week after the first measurement was made with the other incentive, with the objective that the washing period is fulfilled, both measurements will be performed by the principal investigator. For the measurement of the EIT, the instructions defined in standard operating procedure 3 will be followed and for the application of the protocol for the use of incentives, the instructions defined in standard operating procedure 6 and 7 will be followed according to the corresponding incentive. The duration of this procedure will be approximately 30 minutes for each measurement.

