## Objectives and Hypotheses

### General Objective

To compare the distribution of pulmonary ventilation by Electrical Impedance Tomography (EIT) during the use of the Modified Pachon's incentive (Incentivo Modificado de Pachon (IMP) by the name in Spanish) and a Branded respiratory incentive “Triflo II®”, in healthy volunteers from the City of Cali (Colombia).

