### Population Sample

Sample size of 18 subjects (9 men, 9 women) healthy volunteers from the Municipality of Santiago de Cali. The type of sampling will be non-probabilistic for convenience.

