**Exclusion criteria:**

- People with pacemakers, cardioverters or cardio defibrillators.
- People with metal implants
- People with any condition in which the registration in the CT scanner signal is low.
- Women in pregnancy
- Participants with injuries, skin changes or presence of devices that prevent the placement of the electrode belt around the chest.
- People with a high level of physical activity according to the IPAQ questionnaire short version
- People whose spirometry registers obstruction or restriction
- People who do not understand the verbal command of the incentive technique

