### Main variables:

- EELI Delta ( $\Delta$ EELI): Measures the change in the average end-expiratory pulmonary impedance before and after an intervention.
- MTV ROI: Minute regional tidal variation

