## **Phase 4: Statistical analysis**

### Descriptive Analysis

The registration of the information will be carried out in the data collection formats designed for this purpose. To then be organized in the Microsoft Excel program. In order to have an initial knowledge of the behavior of each of the variables.

Quantitative variables will be presented as mean and standard error, and qualitative variables as frequencies and percentages. Normality tests (D'Agostino Pearson) will be applied to identify data distribution; subsequently, a paired T test will be performed to identify if the changes obtained after the interventions are statistically significant ( $p$  less than 0.05). For the statistical procedure, GraphPad Prism version 7.0 will be used.

For the EIT data, the monitoring sessions will be recorded with the participant's code, each recording will be transferred to a USB to be downloaded to the equipment where the information collected is stored for the reconstruction of the impedance measurement through the tool (Electrical Impedance Tomography Data Analysis Tool v6.3, Dräger Medical). This Reconstruction will allow us to isolate the main areas of interest (EIT measurement times) and quantify the percentage changes in EELI in response to lung expansion with respiratory incentive.

Anexo 1. Approval by a human subjects protection review board

Proyecto: **“DISTRIBUCIÓN DE LA VENTILACIÓN PULMONAR CON EL INCENTIVO MODIFICADO DE PACHÓN VS OTRO INCENTIVO RESPIRATORIO COMERCIAL, A TRAVÉS DE TOMOGRAFÍA DE IMPEDANCIA ELÉCTRICA, EN POBLACIÓN SANA DE LA CIUDAD DE CALI”**

Investigador Principal: **“[name]/ [name]/ [name]”**

Código Interno: (031-022)

Fecha en que fue sometido:

DIA	MES	AÑO
16	05	2022

El Consejo de la Facultad de Salud de la Universidad del Valle, ha establecido el Comité de Ética en Investigación en Salud (CEIS), el cual está regido por la Resolución 008430 del 4 de octubre de 1993 del Ministerio de Salud de Colombia por la cual se establecen las normas científicas, técnicas y administrativas para la investigación en salud; los principios de la Asamblea Médica Mundial expuestos en su Declaración de Helsinki de 1964, última revisión en 2013; y el Código de Regulaciones Federales, título 45, parte 46, para la protección de sujetos humanos, del Departamento de Salud y Servicios Humanos de los Institutos Nacionales de Salud de los Estados Unidos 2000. Este Comité certifica que:

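### The crossover plan states no period-adjusted comparison of the two devices, and simple randomization of 18 people does not guarantee a 9:9 order split

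*Combined protocol and SAP*

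**What the plan says.** **Order.** Every participant uses both devices, one week apart. According to the Randomization section, the choice of first device "will be carried out by simple randomization". Two web addresses are cited, one ending in lists/ and the other in permute.htm. No block size, ratio or target for the two orders is given. Population Sample sets 18 participants, 9 men and 9 women; that split is by sex, not by order.

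**Aim.** The General Objective is a comparison of the IMP with the Triflo II.

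**Test.** Under Phase 4, Descriptive Analysis names one inferential procedure: "subsequently, a paired T test will be performed to identify if the changes obtained after the interventions are statistically significant", at p below 0.05. The same section later says that the reconstruction of the recordings will quantify "percentage changes in EELI in response to lung expansion with respiratory incentive". No period or order term appears.

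**Outcomes.** Main variables lists Delta EELI ("Measures the change in the average end-expiratory pulmonary impedance before and after an intervention") and a regional tidal measure, given only as "MTV ROI: Minute regional tidal variation" with no reference to a baseline.

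**The concern.** The test can be read in two ways, and each leaves a gap.

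1. **Pre versus post within each device.** The sentence on percentage changes in EELI supports this reading. The comparison that the trial exists to make then has no stated test. Two within-device p-values do not compare devices, so the method would be chosen after the data are seen.
2. **IMP versus Triflo II within person.** The contrast is then right, but the two visits are a week apart and the test ignores any difference between first and second visit. If the orders are unequal in number, part of a period effect is read as a device effect. Even if they are equal, the period effect is left in the error term and widens the interval.

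The kind of period effect that matters differs by outcome. Delta EELI is a before/after change, so a shift in the day's baseline cancels and only a changed response between visits counts. The regional tidal measure is not defined as a change, so a plain level shift between visits could also enter.

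**Working it through.** All figures below apply to the second reading only.

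**Inputs.** From the documents: n = 18, two periods, p below 0.05 (taken as two-sided). The documents give no SD, effect size, power or period effect, so the 18 cannot be reproduced. Assumed: SDd, the SD of the within-person device difference apart from period effects, is set to 1; period effect π = 0, 0.25 or 0.5 SDd; device effect δ = 0.7 SDd where power is quoted.

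**Step 1: how often the orders are unequal.** If each order is an independent coin flip, the number in one order is Binomial(18, 0.5):
- P(9:9) = 0.185
- P(11:7 or worse) = 0.481
- P(12:6 or worse) = 0.238, so P(11:7 or closer) = 0.762

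A shuffled list of nine of each order gives 9:9 every time.

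**Step 2: bias given the split.** With n1 and n2 people in the two orders, the paired mean estimates δ + π(n2 − n1)/18. At 12:6 the fraction is 6/18 = 0.333, so the bias is 0, 0.083 or 0.167 SDd for the three values of π. Over all splits the mean of |n2 − n1|/18 is 0.1855, so the average absolute bias is 0, 0.046 or 0.093 SDd. The 95% half-width is about 0.5 SDd.

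**Step 3: inflation of the paired standard error.** The factor is √(1 + π²[1 − ((n2 − n1)/18)²] × 18/17). At 9:9 with π = 0.5 this is √(1 + 0.25 × 18/17) = 1.125. With π = 0.25 it is 1.033. At 12:6 the values are 1.111 and 1.029.

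**Step 4: type I error of the paired test** (simulation, 200,000 runs per cell):

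| Split | π = 0 | π = 0.25 | π = 0.5 |
|---|---|---|---|
| 9:9 | 5.0% | 4.3% | 2.9% |
| 10:8 | 5.0% | 4.4% | 3.3% |
| 11:7 | 5.0% | 4.9% | 4.6% |
| 12:6 | 4.9% | 5.7% | 7.0% |

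The 4.9% at 12:6 with π = 0 is simulation error around 5%. Weighted over all splits, type I error is about 5% for each π. The adjusted test stays at about 5% at every split and period effect tried.

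**Step 5: power at δ = 0.7 SDd:**

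| Allocation | Test | π = 0 | π = 0.25 | π = 0.5 |
|---|---|---|---|---|
| Simple, averaged over splits | paired | 80% | 78% | 71% |
| Simple, averaged over splits | period-adjusted | 77% | 77% | 77% |
| Forced 9:9 | paired | 80% | 78% | 72% |
| Forced 9:9 | period-adjusted | 79.6% | 79.6% | 79.6% |

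The averages hide loss at a particular split. At 12:6, with π = 0.5 acting against the device effect, paired power is 48%, against 75% adjusted.

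**Step 6: price of adjustment when π = 0.** Degrees of freedom fall from 17 to 16. The ratio of adjusted to paired SE is 0.5√(1/n1 + 1/n2) / √(1/18), which gives 1.000 at 9:9, 1.006 at 10:8, 1.026 at 11:7 and 1.061 at 12:6. Under simple randomization, power falls as follows:
- δ = 0.5: from 51.6% to 49.1%
- δ = 0.7: from 79.9% to 77.1%
- δ = 0.9: from 94.9% to 93.3%

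For all three, the two tests break even at π of about 0.25 to 0.3 SDd.

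**The case against.** The strongest reply is that the harm on the second reading is assumed. No period effect is given and it may be zero. The protocol also limits practice effects: an instruction video, visual feedback, an intra mark at the end of the third series, exclusion of people who cannot follow the technique, and the same investigator at both visits. A paired t-test in a randomized crossover is legitimate and holds its level on average. Adjustment loses about 3 points of power under simple randomization if there is no period effect. All of this stands, and it is why the point is a robustness improvement and not a defect that invalidates the design. Since the period effect is unknown, though, the choice belongs in the plan. At 9:9 the adjusted test costs almost nothing.

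The cited permute.htm page may mean that a balanced list was intended. That is fair, and if so the imbalance problem goes away. The text still calls it simple randomization, and a 9:9 list does not supply a period term.

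The regional tidal measure may be analysed as a change from the pre mark, in which case a level shift cancels there too. The documents do not settle this, so that risk is possible but not established.

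The Hypothesis section frames the claim as similarity, whereas the error rates above are for a test of difference. They describe the test that the plan states and do not carry over to a similarity test. The confidence interval requested below serves either claim.

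Finally, the missing between-device test on the first reading has nothing to do with period effects, and the figures do not bear on it. It is a gap in its own right.

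**Conclusion.** The concern holds. As written, the plan either states no test of the device comparison or states one without a period term, and it does not secure equal numbers in the two orders. The first gap needs no assumption about period effects.

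The size of the second depends on the period effect: nothing at zero, small at 0.25 SDd, moderate at 0.5 SDd. Among the splits and period effects tabulated, type I error rises above 5% only with both a non-zero period effect and a 12:6 split; 12:6 or worse has a 24% chance if coin flips are really used. At closer splits the cost is a wider interval than necessary. The standard operating procedures for using the two devices are not in the documents, so the extent of familiarization cannot be judged. This should be fixed, but it does not make the trial invalid.

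**What to change.** **Analysis text (applies even if randomization is complete).** State whether the paired t-test is pre versus post within a device or between devices. State that Delta EELI and MTV ROI will be compared between devices with adjustment for period. Either of these would do:
- a two-sample t-test comparing the period 1 minus period 2 differences between the two orders, with the estimate and its standard error halved;
- a mixed model with device, period and participant.

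Report the confidence interval and the realized order split.

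**Randomization text.** Say whether the list is balanced. If it is not, and randomization is still open, replace simple randomization with a permuted list giving 9:9 overall.

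**Cost.** One or two sentences, no new data, and an unpaired t-test is enough. The statistical price is the one in Step 6: about 3 points of power at 0.7 SDd under simple randomization with no period effect, or about 0.3 points (79.9% to 79.6%) with a 9:9 list. In return, about 6 points are gained under simple randomization if the period effect is 0.5 SDd (70.6% to 77.1%).

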## Ethical aspects

According to the Declaration of Helsinki, the ethical principles for medical research on human beings, including the investigation of human material and identifiable information, and according to the scientific and technical standards established in Resolution 8439 of 1993, for health research, and according to its Article 11. This research is classified with a minimum risk due to the fact that in this project common procedures will be carried out, such as the anthropometric measurement of the height and weight of the subject in a healthy volunteers, deep and forced breathing maneuvers will be requested that are not expected to have adverse events since the patients are healthy and these procedures do not represent physical or psychological risks. however, for the study, the measurements will be made in a space with a flat floor, with adequate beacons and accompaniment of the researchers in order to mitigate the risk of falls.

Complications of forced spirometry are rare. The most common are coughing fits, bronchospasm, chest pain, dizziness, urinary incontinence or increased intracranial pressure. Very rarely, the patient may experience syncopal symptoms. For this, the spirometry will be performed at the Hospital Universitario del Valle, by a professional trained and experienced in performing these, and in the event of any of these events, the test will be suspended and If the symptoms do not subside, the emergency service will be consulted directly. This test will be performed to rule out the coexistence of any alteration in lung function.

In general, there are very few risks or possible complications with the incentive spirometer, but it is important to stop if you feel dizzy. However, there are rare reports of pneumothorax that have been associated with very aggressive spirometry in people with emphysema (and pulmonary bullae that could rupture), in this case if the patient is uncomfortable the test will be discontinued, the other major risks were ruled out with the result of the spirometry in a normal state, in addition, the technique will be performed and guided by the researcher, who is a physiotherapist with experience in handling the technique and trained in case of any eventuality.

The IMP is a device for therapeutic use, which has an industrial design registration, granted by the Superintendence of Industry and Commerce to the Universidad del Valle under the name of "Inspirometro". So its use is supported.

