### **Moments of electrical impedance tomography measurement**

Once the patient is connected to the tomograph, the quality of the signal must be checked. Once it is verified that it is being measured properly, that the patient is well positioned and that the signal is of high quality, the recording will begin. tomograph record; after the first

two minutes of calm breathing have elapsed, the first event will be marked, which will be recorded as "pre", and the use of the corresponding respiratory incentive will begin. The proper use of the device will be previously explained to you through a video that will illustrate the correct way to use it. The participant will receive visual feedback from the device when the condom is raised within the buretrol in the case of the IMP or when the spheres are raised in the branded incentive "Triflo II®"

Three series of ten breaths will be performed, with a 1-minute rest between series. In the last repetition of the third series, the second event will be marked, which will be recorded as "intra".

The maneuver will be finished once the series and repetitions are finished, removing the mouthpiece from the participant's mouth and they will be asked to continue breathing calmly for 2 minutes, after which the third event will be marked, which will be recorded as "post". And the recording of the record will be terminated.

At the beginning and at the end of the intervention, clinical data will be taken (heart rate, respiratory rate and oxygen saturation) and 15 minutes after finishing the test.

Taking into account that the subjects are using a device that is not used routinely in daily life, the perception of the subject in the use of each of the devices will be evaluated to know the degree of comfort of these by means of the scale of Likert and in the same way it will be valued if I generate perception of dyspnea by means of the Borg scale

The session may be interrupted if the participant does not wish to continue with the intervention, if the participant shows intolerance to the maneuver, if the respiratory rate is greater than 25 breaths per minute and if there is use of accessory muscles.

After each measurement is finished with each participant, the equipment will be disinfected

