#### **Quality control:**

1. To guarantee the quality of the registered information, the main investigator will carry out random reviews in which he will corroborate the coherence between the original information of the tomographer, that of the registration in the formats and that of the database. The detected errors will be corrected.
2. An external person to the study, who will not participate in the measurements, will randomly review the forms once every 15 days to verify the information before entering it into the database. Additionally, once a month a meeting will be held with the research group in order to socialize project progress

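### EIT values are extracted offline with no step that hides device or period; relabelling the 36 recordings and fixing the extraction rule in advance would cheaply close an avoidable route to bias.

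*Combined protocol and SAP*

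**What the plan says.** - **Sessions.** Each volunteer uses one device, then the other a week later, and "both measurements will be performed by the principal investigator" (Randomization). Under Ethical aspects, "the technique will be performed and guided by the researcher, who is a physiotherapist with experience in handling the technique". Whoever runs a session knows the device.
- **Event marks.** The section on moments of EIT measurement sets three marks: 'pre' after two minutes of quiet breathing, 'intra' during the manoeuvre ("In the last repetition of the third series, the second event will be marked"), and 'post' after two further quiet minutes. It does not name the person who sets them.
- **Extraction.** Descriptive Analysis (Phase 4) has the recordings filed under the participant's code, moved by USB and reconstructed in the manufacturer's tool. The purpose is to "isolate the main areas of interest (EIT measurement times") and to quantify percentage change in EELI. Operator, window length, breath selection and artefact handling are not given.
- **Code.** Ethical aspects describes a four-digit sequential code whose last two digits come from the date. It is listed among the confidentiality measures.
- **Checks.** Under Quality control, "the main investigator will carry out random reviews in which he will corroborate the coherence between the original information of the tomographer", the forms and the database. It adds: "The detected errors will be corrected". "An external person to the study, who will not participate in the measurements" reviews the forms every 15 days before data entry.

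The supplied text nowhere mentions masking of the operator, the EIT reader, the person who corrects data or the analyst.

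**The concern.** ΔEELI, one of the two main variables, is a change in an average. Its value depends on which stretch of the recording is averaged and which breaths are set aside as artefact. If those decisions are made by someone who knows which device produced the trace, they can differ systematically between devices. Randomised order balances period effects, but it does not touch an error that follows the device.

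Both directions matter. A shift away from zero can create a difference that is not there. A shift toward zero can hide a real one, and the alternative hypothesis of this trial is that the two devices are similar. Unlike the session itself, the extraction step can be masked, so this exposure is avoidable.

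**Working it through.** **1. What is fixed and what is left open**

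| Step | Stated in the plan | Not stated |
|---|---|---|
| Running the session | Principal investigator, both devices | – |
| Timing of the marks | Fixed for 'pre', 'intra', 'post' | Who sets them |
| Extraction | Offline, in the manufacturer's tool | Who does it; seconds or breaths averaged; artefact rule; whether device and period are hidden |
| Coherence review | Main investigator, on a random selection | Who makes the corrections; whether they are logged |
| External review | Forms, every 15 days | Any check of recordings or windows |

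The remaining discretion is therefore not over when the marks fall. It is over what is averaged around each mark, and over exclusions.

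**2. Whether the code masks**

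The code contains no device name. It is sequential, however, and ends in date digits. If it is issued at each session, those digits can point to the period for anyone who knows the schedule. If it is issued once, both recordings of a participant share it and something further must tell them apart; the plan does not say what. Neither reading is a mask.

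**3. Number of recordings**

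18 participants (Population Sample) × 2 devices = 36.

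**4. Illustration of size**

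The plan gives no figure to reproduce: 18 comes without an effect size, SD, power or margin. Inputs from the plan are n = 18, a paired t test and a 0.05 threshold. Assumptions are that the test is two-sided, that it compares the devices, and that there is a systematic device-related shift b in SDs of the paired difference.

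- Standard error of the mean difference = 1/√18 = 0.236 SD.
- Critical value t(0.975, 17 df) = 2.110, so an observed difference of 2.110 × 0.236 = 0.50 SD reaches significance.
- Rejection probability = P(|T| > 2.110), where T is non-central t with 17 df and non-centrality b√18.

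No true difference, shift b:

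| b (SD) | b√18 | False-difference rate |
|---|---|---|
| 0 | 0 | 5.0% |
| 0.10 | 0.42 | 6.9% |
| 0.25 | 1.06 | 17.0% |
| 0.50 | 2.12 | 51.6% |

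True difference 0.70 SD (chosen because it gives about 80% power), shrunk by b:

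| b (SD) | Apparent difference (SD) | Power |
|---|---|---|
| 0 | 0.70 | 79.9% |
| 0.10 | 0.60 | 67.0% |
| 0.25 | 0.45 | 43.7% |

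**The case against.** The strongest reply is that little discretion may exist. The three marks are set by protocol, the isolated measurement times most naturally mean those marks, and EIT measurement follows standard operating procedure 3, which was not supplied and may already define the window. This stands in part. If that procedure contains a rule, that part of the fix becomes a citation. A window rule alone, though, would still leave artefact decisions and corrections open to someone who knows the device.

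A reader might infer several stronger things that the documents do not support:

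- **That windows are chosen manually.** The plan says only that the tool allows them to be isolated. Manual, automatic and mark-driven isolation all fit the wording.
- **That the principal investigator alters the tomograph data.** The tomograph record is the original against which forms and database are compared. The text reads as a transcription check, and no corrector is named.
- **That the same investigator marks the events and extracts the values.** Both are plausible, but neither is stated.
- **That there is a motive.** The university that holds the design registration of the modified incentive also hosts the EIT sessions, but the protocol declares no conflict of interest. The point needs no motive.

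It is also fair to say that the shifts above are assumed, that 0.50 SD is large, and that an unbiased test with 18 participants would itself miss a true difference of 0.10 or 0.25 SD about 93% or 83% of the time (100% − 6.9% and 100% − 17.0%). Finally, the external reviewer is a real safeguard, but for forms only.

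**Conclusion.** The point holds as an inexpensive improvement, not as evidence that the results will be biased. EIT values are derived after unblinded sessions, at a step where the supplied text names no extractor, sets no averaging rule and does not hide device or period. Device-aware decisions there could bias the paired difference either way.

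The size cannot be derived from the documents. The rates of 6.9%, 17.0% and 51.6% show only how sensitive a paired comparison of 18 people is to assumed shifts of 0.10, 0.25 and 0.50 SD. The conclusion rests on the supplied text being complete on masking. Standard operating procedure 3 could narrow the gap on the window rule. Nothing here calls for a change in sample size.

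**What to change.** Add one paragraph to Descriptive Analysis (Phase 4) stating that:

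1. The 36 recordings are relabelled with random codes that hide participant code, device, date and period. The external person already named under Quality control holds the key.
2. Values are extracted in one batch after the last session, by a rule set in advance for each mark and identical for both devices. It covers length or number of breaths, and artefacts. It may differ between the quiet breathing of 'pre' and 'post' and the single manoeuvre breath of 'intra', where a long window would run into quiet breathing. If standard operating procedure 3 has such a rule, cite it.
3. Extracted values and any corrections are logged and locked before the key is opened.
4. Where possible, the extractor is a team member who did not run the sessions. No new reader is required.

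**Cost.** No extra participants, visits or equipment are needed. The data collection form (Materials and Instruments) includes impedance results, and these would be entered only after all sessions, so the 15-day form review must treat the EIT fields separately. The external person gains one small duty, and EIT results arrive later. Masking will be imperfect, because the shape of the 'intra' trace may still hint at the device, but the cues from code and date are removed.
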